#### *Resistance testing:*

Endocervical samples – baseline and follow-up, from both arms – with a positive NAAT result for *C. trachomatis* and/or *N. gonorrhoeae*, will be shipped to the University of Washington laboratory of [name] for molecular testing. DNA will be purified from residual endocervical NAAT samples and endocervical swabs using the *High Pure DNA Kit* (Roche Diagnostics, Indianapolis, IN). The impact of dPEP on *C. trachomatis* and *N. gonorrhoeae* resistance will be measured by comparing the overall rates of doxycycline-resistant events occurring in the dPEP arm to rates in the control arm, at baseline and separately during follow-up adjusted for medical factors that confound the dPEP-resistance risk relationship.

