Acceptability: Quantitative analysis will be completed using GEE to test associations between facilitators/barriers and randomization arm, dPEP adherence, and STI outcomes. Data will be analyzed to understand factors impacting acceptability of dPEP, including demographics, stigma, fertility desire, dPEP effect on sexual and preventative decision making. Qualitative analysis will take a longitudinal approach. Interview discussions will be recorded, transcribed, and translated into English. Transcripts will be reviewed separately by two investigators for completeness and initial theme generation. We routinely use rapid debriefing reports to obtain real-time information; formal coding and analysis will be performed with Atlas.ti, using inductive approach informed by theoretical framework of acceptability (TFA), a recently developed approach to acceptability research of medical interventions. The components of TFA are affective attitude, burden, ethicality, intervention coherence, opportunity costs, perceived effectiveness, and self-efficacy. Initial code generation of the transcript themes will capture experiences and context of dPEP use. Codes will be reviewed for consistency and inter-coder agreement with consensus code generation by themes. Following a similar process, transcripts from Months 6 and 12 will be coded with reference to the baseline codes to capture temporality of experiences and contexts within each participant. Codes generated from transcripts at Months 6 and 12 will be compared across participants to establish differences and similarities across the sample. The code will reflect the longitudinal data and emergence of new codes. Descriptive thematic analyses will be done at baseline and over time.

Resistance: The impact of dPEP on *C. trachomatis* and *N. gonorrhoeae* resistance will be measured by comparing the overall rates of doxycycline-resistant events occurring in the dPEP arm to rates in the

control arm, at baseline and separately during follow-up adjusted for medical factors that confound the dPEP-resistance risk relationship.

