### 2.2. Study Endpoints

#### 2.2.1. Primary Efficacy Endpoints

##### Effectiveness of doxycycline

The primary endpoint is assessed using the following STI endpoints at month 3, 6, 9 and 12 visits:

- Documented positive vaginal/cervical GC
- Documented positive vaginal/cervical CT
- Early syphilis infection based on four-fold increase in non-treponemal titers.

The primary trial endpoint is any newly diagnosed STI, defined as any one of the above after the enrollment visit, with the exception of re-diagnosis of the same infection at a test of cure visit within 28 days of first treatment of a baseline or incident infections (which is considered a non-cured infection and re-treated). Any infection newly diagnosed at an interim visit will be counted as a primary endpoint for the subsequent scheduled visit i.e., if a participant is diagnosed with new GC infection at an interim visit 40 days after their 6 month visit, this will be analysed as a primary 9 month endpoint. Endpoints are reviewed by committee, blinded to study arm, and primary endpoints designated in that review.

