#### 2.2.2. Secondary Efficacy Endpoints

##### Efficacy of doxycycline for individual STIs

Effectiveness of doxycycline will also be assessed for CT and GC separately, using an incident STI definition that parallels the above for the specific infection.

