**Endpoint definitions:**

Primary endpoint: **Any incident STI at Month 3, 6, 9 or 12.** Repeat positive tests for the same STI up to 28 days after treatment of an incident infection (the window for the test of care visit) will not be counted as incident infections. Incident infections detected at interim visits more than

28 days after treatment will be treated in the analysis as if they would have been detected at a scheduled visit (months 3, 6, 9 and 12). Therefore, an STI diagnosed at an interim visit outside the treatment window is carried forward to the next scheduled visit. If a participant has more than one positive STI (different bacterial infections) at a scheduled visit it will be counted as one incident “any STI” event for that visit interval. If scheduled visits are missed, infections will be assigned to the next scheduled visit (i.e., the first missed scheduled visit).

Secondary endpoints: **Any GC, Any CT at Month 3, 6, 9 and 12.** The same approach as defined for the primary endpoint will be used, restricted to each specific bacterial infection.

The criteria for an incident syphilis case will include a four-fold increase in non-treponemal titers (e.g., the RPR) and/or a consistent clinical presentation.

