### **Statistical analysis**

Comparison of STI incidence by arm will be conducted by estimating the relative risks of any STI over the 3, 6, 9 and 12 month visits using a modified Poisson model fitted using GEE methods to account for repeated observations from each participant, assuming an independent covariance structure, with study arm as the only covariate[1]. The test for significance will be a two-sided alpha = 0.05. 95% confidence intervals will be computed using robust standard errors.

The same analysis will be repeated for the individual STIs.

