### **7.7. Analysis of Tetracycline resistance**

#### **7.7.1. Analysis of TCN resistance in GC cases**

TCN resistance will be assessed in GC cases only. TCN resistant GC will be defined by the detection of plasmid-mediated *tetM* gene conferring high-level tetracycline resistance.

Descriptive statistics: Tabulations of resistance (No GC, GC: TNC resistance testing = missing, not resistant, resistant) will be reported at baseline, 3, 6, 9 and 12 month visits in GC cases in each arm.

Statistical analysis: Assessment of odds of resistance by arm will be assessed by estimating the odds of GC infection with resistance among cases detected after enrollment using logistic regression, adjusted for visit.

Sensitivity analysis: molecular chromosomal mutations may lead to expression of tetracycline resistance. Tabulations of number of expressed chromosomally-mediated tetracycline resistance determinants (*mtrR*, *rpsJ*, *porB*, and *pilQ*) will be reported at baseline, 3, 6, 9, and 12-

month visits in GC cases, among those with or without plasmid-mediated tetracycline resistance (i.e., detection of *tetM*), in each arm.

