### **7.7.2. Analysis of TCN resistance in CT cases**

The analysis of TCN resistance in CT cases will include all positive CT cases after baseline. TCN resistant CT will be defined by the detection of *tetC* gene cassette.

Descriptive statistics: Tabulations of TCN resistance in CT cases (TNC resistance testing = missing, not resistant, resistant) will be reported at baseline, 3, 6, 9 and 12 month visits in each arm.

Statistical analysis: Assessment of difference in odds of TCN resistance by arm across all post baseline visits with infection will be assessed by estimating the odds of TCN resistance using logistic regression, with repeated measures methods (GEE) if repeat infections occur.

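### SAP 7.7 compares arms only on the odds of resistance among infected women, while the protocol plans a comparison of rates of resistant events without a denominator; define the rate, add it, and cluster the GC model

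*SAP*

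**What the plan says.** **Protocol.** The Resistance testing section describes the plan as "comparing the overall rates of doxycycline-resistant events occurring in the dPEP arm to rates in the control arm". This is done once for baseline and once for follow-up, with adjustment for unnamed medical confounders. Section 10.0 (Secondary Analyses, Resistance) repeats the plan: "comparing the overall rates of doxycycline-resistant events occurring in the dPEP arm". Neither place says whether the rate is per woman, per person-time, per visit or per positive sample. The secondary outcomes count tet(M) and/or other tetR determinants.

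**SAP models.** Section 7.7.1 defines resistant GC by tet(M) alone and specifies "estimating the odds of GC infection with resistance among cases detected after enrollment using logistic regression, adjusted for visit". Section 7.7.2 specifies, for CT, "estimating the odds of TCN resistance using logistic regression, with repeated measures methods (GEE) if repeat infections occur". The analysis populations (5.2.4, 5.2.5) are post-baseline positives only.

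**SAP tables.** Section 7.7.1 tabulates GC by visit and arm, with categories for no GC, missing result, not resistant and resistant. The CT table has no uninfected category. No rate ratio or confidence interval follows from either.

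**What counts as a case.** SAP 2.2.5 builds the resistance endpoint on positive swabs from scheduled visits and also from any test-of-cure visit. The efficacy endpoint is different. Section 2.2.1 counts new diagnoses "with the exception of re-diagnosis of the same infection at a test of cure visit within 28 days of first treatment", Section 2.2.2 carries this to single pathogens "using an incident STI definition that parallels the above for the specific infection", and Section 7.5.1 leaves out the following: "Repeat positive tests for the same STI up to 28 days after treatment of an incident infection".

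**Primary model.** Section 7.5.1 uses a "modified Poisson model fitted using GEE methods to account for repeated observations from each participant", with arm as the only covariate, and repeats it for the individual STIs.

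**The concern.** Becoming a GC or CT case happens after randomisation and can be changed by dPEP. An odds ratio among cases therefore describes the resistant share of the infections that still occur. It does not say whether women assigned to dPEP acquire more resistant infections than controls, which is the natural reading of a comparison of rates between arms.

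The question carries weight in the documents. Resistance is a primary objective in the protocol and a secondary objective in the SAP. The protocol lists a significant change in the rate of resistant STIs among the DSMB's grounds for recommending a stop, and SAP 4.1 weighs acquired resistance against stopping for efficacy.

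Two practical weaknesses add to this. The logistic models may have empty cells, and no sparse-data method is named. The GC model also names no clustering by participant, so repeat positives from one woman, including a test-of-cure positive from the same infection, could be treated as independent observations.

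**Working it through.** **Plan's own figures.** The documents give no event count, effect size or power for the resistance comparison, so there is nothing to reproduce on that point. The design inputs do reproduce. For a 50% reduction, events = 4 × (1.960 + 0.842)² / (ln 0.5)² = 65.3, rounded up to 66 (SAP 3.3.1). Then 66 / 0.165 / 0.9 = 444.4, against the stated 446, where 0.165 is the mean of 22% and 11%.

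**Inputs.** 223 women per arm and 10% loss (SAP 3.3.1), taken as 223 × 0.9 = 200.7 person-years per arm. GC incidence 11/14/20% per year (protocol Table 3). Resistant share r from 73% (low end of the African range in the protocol background) to 96% (48/50 preliminary Kenyan samples). The dPEP effects below are illustrative assumptions.

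**1. The two measures differ.** With R resistant and S susceptible GC events, the case-only OR is (R1/S1)/(R0/S0) and the rate ratio is R1/R0. At r = 73% and incidence 11%, the control arm expects R = 200.7 × 0.11 × 0.73 = 16.1 and S = 200.7 × 0.11 × 0.27 = 6.0.

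| Assumed dPEP effect | dPEP arm R / S | OR among cases | Resistant-GC rate ratio |
|---|---|---|---|
| Prevents 50% of susceptible GC only | 16.1 / 3.0 | 2.00 | 1.00 |
| Prevents 50% of all GC | 8.1 / 3.0 | 1.00 | 0.50 |
| Prevents 90% of susceptible, 20% of resistant | 12.9 / 0.6 | 8.00 | 0.80 |

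The ratios do not depend on the incidence or on r.

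**2. How often the OR would be significant.** Row 1 was simulated (40,000 trials per setting, Wald test, no visit adjustment). A significant OR above 1 occurs in 7/11/19% of trials at 73%, in 1/2/5% at 86.3% (the lower exact limit for 48/50), and in about 0% at 96%.

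**3. Empty cells, GC.** Susceptible cases per arm are taken as Poisson with mean m = 200.7 × incidence × (1 − r). At r = 96%, m = 0.88/1.12/1.61. P(at least one arm empty) = 1 − (1 − e^−m)² = 66/54/36% if dPEP has no effect on GC. With the 275 per arm of protocol Section 10.0 it is 56/44/26%. If susceptible GC is halved on dPEP, the 223-per-arm figures become 79/71/56%. At r = 73% with no effect they are 0.5/0.1/0.0%.

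**4. Does the planned all-GC model stand in?** Under row 1 the all-GC RR is r + (1 − r) × 0.5, which is 0.98 at 96% and 0.87 at 73%, against a resistant-GC RR of 1.00.

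**5. What a resistant-GC rate ratio would deliver.** Expected resistant cases per arm are 16.1/20.5/29.3 at 73% and 21.2/27.0/38.5 at 96%. The expected 95% CI at a true RR of 1 is exp(±1.96 × √(2/mean)). It runs from 0.50–1.99 (73%, incidence 11%) to 0.64–1.56 (96%, incidence 20%). Power (two-sided 0.05, simulated Poisson counts):

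| True RR | 73% tet(M) | 96% tet(M) |
|---|---|---|
| 1.2 | 8–11% | 9–13% |
| 1.5 | 23–39% | 29–50% |
| 2.0 | 64–88% | 76–95% |

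A robust-variance Poisson GEE on 201 women × 4 visits per arm gave similar values for RR 1.2 and 1.5 (for RR 1.5, 24–41% and 31–52%).

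**6. CT.** If no tet(C) is found, as in the preliminary 0/10, the logistic OR cannot be estimated. The exact 95% upper limit for 0/n is 1 − 0.025^(1/n). Table 3 CT incidence of 27–53% gives 54–106 control cases and limits of 6.6–3.4%. Halved to 27–53 cases on dPEP, the limits are 12.8–6.7%. At the design minimum of 44 and 22 cases they are 8.0% and 15.4%.

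**The case against.** The strongest reply is that the two documents may not conflict. Only NAAT-positive samples are tested for resistance, the protocol applies its rates at baseline too, where there is no person-time, and its objective concerns resistance in the organisms. A proportion among positives is therefore a fair reading of rates. This stands, so a reader should not infer that the SAP plainly breaches the protocol. It does not remove the need to state the denominator.

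For GC, the planned table already supplies uninfected and missing categories by visit and arm. That also stands; what is missing is an estimate with its interval.

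The gain is modest near 96% tet(M), where the all-GC model is a near substitute. The protocol itself doubts that dPEP works against GC, and with no effect on GC neither measure would be distorted. A significant OR in the halving scenario would correctly detect a true OR of 2, and the SAP words it as an odds among cases. What remains is the risk that it is read as added resistance. That risk needs the 73% end of the range and an assumed halving of susceptible GC.

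A reader might also infer that the 28-day test-of-cure exclusion already defines a case in 7.7 and settles double counting, or should be extended to do so. The documents do not support this. The exclusion belongs to the efficacy endpoint, and SAP 2.2.5 deliberately places test-of-cure swabs in the resistance endpoint.

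**Conclusion.** The concern holds as a gap in a secondary analysis that should be closed. SAP 7.7 contains no between-arm rate of resistant infection, and the protocol does not define the one it plans. The case-only odds ratio answers a narrower question, and its two weaknesses arise at opposite ends of the cited tet(M) range. Near 96% it is often not estimable (an empty susceptible cell in 36–66% of trials with no dPEP effect on GC). Near 73% it can be significant with no added resistant GC (7–19% of trials under the assumed halving). The CT odds ratio cannot be estimated with zero tet(C). The missing clustering term for GC is a plain omission, given the CT wording and the inclusion of test-of-cure swabs.

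These sizes rest on 223 per arm, 10% loss, Table 3 incidences and Poisson counts. Two stronger readings are not supported. No efficacy conclusion changes. Nor would the added rate ratio settle the resistance question, because its power is low for anything short of roughly a doubling.

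**What to change.** In SAP 7.7:

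1. Add a between-arm rate ratio of tet(M)-positive GC per randomised participant-visit, using the 7.5.1 modified Poisson GEE. State the denominator and how GC-positive visits with a missing resistance result are counted. Report the estimate and its confidence interval, and say that power is low.
2. Keep the case-only odds ratio as supporting, labelled conditional on infection. Cluster by participant for GC as for CT, and use Firth or exact estimation when data are sparse. Where a cell is zero, for example tet(C) in CT, report exact confidence bounds by arm.
3. Align 7.7 with 2.2.5. Keep test-of-cure swabs in the resistance tables, and state that a test-of-cure positive belongs to its index infection and is not a separate event in the models.
4. Reconcile the remaining differences from the protocol: tet(M) alone against tet(M) and/or other tetR determinants; the adjustment set (visit for GC and no named covariate for CT, against medical confounders); and the baseline comparison, for which the SAP has only tables.

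The cost is SAP wording and one more model on data already collected, with no new samples or visits. The downside is one additional low-power secondary analysis.

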**State-of-the-art assessment of antimicrobial resistance.** Over the past 14 years, [name] has worked extensively in the field of gonococcal antimicrobial resistance (AMR). [name] laboratory characterizes molecular mechanisms of AMR in *N. gonorrhoeae* isolates and is a core laboratory for CDC's national gonococcal AMR surveillance project, and he has identified isolates with unique AMR profiles. Preliminary results from frozen STI+ endocervical swab samples from Kenyan women in our Partners PrEP Study (i.e., \*not\* using dPEP) were tested for tetracycline resistance using the molecular methods: 50 with *N. gonorrhoeae* and 10 with *C. trachomatis*. Detection of tetracycline-resistance was high for *N. gonorrhoeae* (*tet*(M)=48/50, 96%), suggesting resistance may be at a ceiling in the community already, prior to dPEP use, but also that dPEP may not be effective against *N. gonorrhoeae*. No *C. trachomatis* organisms had resistance (*tet*(C)=0/10, 0%).

**Mathematical modeling and costing studies help to define optimal models for PrEP delivery.** Led by [name], we have used costing methods and mathematical modeling to address key questions related to how to best deliver PrEP. For serodiscordant couples, we found the cost of PrEP per infection averted is significantly offset by future savings in ART costs, especially time-limited PrEP – used prior to and early after ART initiation by an HIV infected partner, when risk is highest. These results were a key basis for designing our “PrEP as a bridge to ART” strategy in the Partners Demonstration Project. Second, we used methods for development of clinical prediction rules to derive a risk scoring tool for couples. Our work has been a model for risk scores for other populations – for example, the VOICE score for women at risk – and for programmatic prioritization of subpopulations for PrEP. Third, micro-costing, time and motion work, and mathematical modeling have helped define the annual cost of PrEP (~US\$100) for the Kenya Ministry of Health.

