### Statistical power and analysis

We propose a standard randomized superiority design, comparing dPEP to standard of care. The primary trial outcome will be the combined incidence of incident *C. trachomatis*, *N. gonorrhoeae*, and syphilis, compared between the randomization arms, to mirror the IPERGAY approach; analyses will also test each pathogen alone. We have been conservative in planning: first, we have planned for an STI incidence of 22% per year in the standard of care arm, which is less than the *C. trachomatis* incidence seen in our recent studies (**Table 3**) and second, we will calculate based on time to first incident STI alone, although we anticipate that some women will have repeat STIs contributing additional events and additional statistical power. We have planned for a 50% effect, comparable to the IPERGAY results and sufficiently great for public health benefit, but we anticipate that the *C. trachomatis* effect could be >50%, given universal susceptibility to doxycycline and

IPERGAY findings. With 80% power, 10% loss-to-follow-up, incidence of 22% vs. 11% (n=44 vs. 22 cases), and a two-sided alpha of 0.05, a sample size of n=550 is needed (n=275 per arm).

*Primary Analysis:*

We will analyze the composite endpoint of any of the three STIs as well as for *C. trachomatis* alone, and we will continue until there are sufficient *C. trachomatis* events (n=66) given the high incidence of this pathogen and its importance for reproductive morbidity (the consequence of which will be that the total number of events in the composite of *C. trachomatis*, *N. gonorrhoeae*, and syphilis will be greater than n=66). Analyses will be intention-to-treat, including women whether or not they continue dPEP (as well as whether or not they continue PrEP). STI incidence will be compared between arms using repeated measures analysis of proportions (e.g., generalized estimating equations [GEE]), given possibility of repeat infection within individuals. Per-protocol and adjusted analyses will be done as needed, controlling for potential confounders: demographics (e.g., age, education), sexual behavior (e.g., condom use, # partnerships), and beliefs (e.g., risk perception, dPEP/PrEP efficacy). SAS or R will be used.

*Secondary Analyses:*

Safety: Safety outcomes (i.e., AEs, tolerability, pregnancy, behavior) will be compared between arms using repeated measures analyses.

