### **2.2.5. Tetracycline resistance**

- Molecular markers of resistance for CT after enrollment (positive CT swabs collected at Enrollment, Month 3, 6, 9 and 12, as well as any test of cure visits)
- Molecular markers of resistance for GC after enrollment (positive GC swabs collected at Enrollment, Month 3, 6, 9 and 12, as well as any test of cure visits)

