#### **5.2.4. GC positive Population**

Post-baseline GC positive participants assessed for TCN resistance. All participants with positive GC will be assessed for molecular resistance

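### The GC resistance model in SAP 7.7.1 has no provision for several results from one woman, and no fallback if nearly all GC cases carry tet(M)

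*SAP*

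**What the plan says.** SAP 7.7.1 defines a resistant GC case by detection of plasmid-borne tet(M). It estimates the odds of resistance by arm in post-enrolment cases "using logistic regression, adjusted for visit". It names no cluster term, GEE or robust standard error, does not say whether visit is categorical or linear, and gives no alternative if the model cannot be fitted.

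The neighbouring analyses differ:

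- SAP 7.7.2 (CT resistance) uses logistic regression "with repeated measures methods (GEE) if repeat infections occur", without visit adjustment.
- The primary efficacy model in SAP 7.5.1 is "fitted using GEE methods to account for repeated observations from each participant".
- The Protocol (Statistical power and analysis) chose repeated-measures methods for STI incidence "given possibility of repeat infection within individuals".

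Two passages bear on what counts as one observation. SAP 2.2.5 takes resistance results from positive swabs at scheduled visits "as well as any test of cure visits". SAP 5.2.4 defines the GC population by person: "Post-baseline GC positive participants assessed for TCN resistance".

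On expected resistance, the Protocol background reports tet(M) in 48 of 50 stored Kenyan GC samples, "suggesting resistance may be at a ceiling in the community already". It also cites 73-97% for plasmid-mediated tetracycline-resistant GC in Africa.

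**The concern.** There are two separate weaknesses.

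The first is clustering. Arm is constant within a woman. If she contributes two or more GC results with positively correlated tet(M) status, a model that treats them as independent gives too small a standard error for the arm effect. A test-of-cure positive is the clearest risk, because SAP 2.2.1 regards re-diagnosis of the same infection at test of cure within 28 days as a non-cured infection.

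The second is sparse data. If nearly every GC case carries tet(M), one arm may have no non-resistant case at all. The maximum likelihood odds ratio is then infinite, or undefined if neither arm has one.

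The stakes are moderate. Resistance in GC and CT is objective 4 of the Protocol. A significant change in resistant STIs is among the grounds on which the DSMB may recommend stopping, and SAP 4.1 requires stopping for efficacy to be weighed against evidence on acquired resistance. The Protocol says doxycycline resistance has never been reported in CT, so GC is where resistance will be seen. If the stated model fails and nothing replaces it, the method would be chosen after the data are known, in an open-label trial.

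**Working it through.** **The plan's own figure.** 48/50 = 0.96; the exact 95% interval is 86.3% to 99.5%. The documents give no power or precision figure for the resistance comparison.

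**Inputs from the documents.** 223 women per arm (SAP 3.3.1); GC incidence 11%, 14% and 20% per year (Protocol Table 3); resistance 96% and 73%, with 90% added as an intermediate value.

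**Assumptions not in the documents.** Mean follow-up of 0.95 year per woman; cases spread evenly over four visits; no dPEP effect on GC incidence or resistance; the within-woman correlations and the spread of risk between women used below.

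**Expected cases.** Per arm, 223 x 0.95 x incidence = 23.3, 29.7 and 42.4. Over both arms that is about 47, 59 and 85. At 96% resistance the non-resistant cases number 0.04 x 46.6 = 1.9, 0.04 x 59.3 = 2.4 and 0.04 x 84.7 = 3.4.

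**Can the arm odds ratio be estimated?** Without visit in the model, it fails when at least one arm has no non-resistant case. With a Poisson mean of m non-resistant cases per arm, the probability is 1 - (1 - e^-m)^2. At 96%:

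- 11% per year: m = 0.93, 1 - (1 - 0.394)^2 = 63%
- 14% per year: m = 1.19, 1 - (1 - 0.305)^2 = 52%
- 20% per year: m = 1.69, 1 - (1 - 0.184)^2 = 33%

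A simulation of 1,500 trials per setting, with a formal check for separation, gives the share of trials in which the arm odds ratio is not estimable:

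| Resistance | GC incidence | Visit in model (4 levels) | Arm only |
|---|---|---|---|
| 96% | 11% | 63.3% | 63.1% |
| 96% | 14% | 51.8% | 51.7% |
| 96% | 20% | 34.0% | 34.0% |
| 90% | 11% | 18.9% | 18.7% |
| 90% | 14% | 9.0% | 8.9% |
| 90% | 20% | 3.2% | 3.2% |
| 73% | 11% | 0.3% | 0.3% |
| 73% | 14% or 20% | 0.0% | 0.0% |

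At 96%, at least one visit has no non-resistant case in 98%, 97% and 90% of trials, so a categorical visit term is infinite. The near-identical columns show that this is not what removes the arm estimate.

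With the Protocol's 275 per arm and 96% resistance, m = 275 x 0.95 x 0.11 x 0.04 = 1.15 gives 53%, and m = 275 x 0.95 x 0.20 x 0.04 = 2.09 gives 23%.

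**Effect of ignoring clustering.** Design effect = 1 + (m* - 1) x rho, where m* is the size-weighted mean number of GC cases per infected woman. If all women have the same risk, m* = 1 + incidence. If risk varies as a gamma distribution with shape k, m* = 1 + incidence x (1 + 1/k).

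- Low: 11%, same risk, rho 0.2: 1 + 0.11 x 0.2 = 1.022; square root 1.011, so the standard error rises 1%.
- High: 20%, k = 1, rho 0.5: 1 + 0.40 x 0.5 = 1.20; square root 1.095, so it rises about 10%.
- Extreme: 20%, k = 0.5, rho 1: 1 + 0.60 = 1.60; square root 1.265, so it rises 27%.

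Expected repeat cases are 2.5 to 7.9 with the same risk for all, and 4.6 to 14.1 with k = 1. Test-of-cure swabs are not included. Counting them as cases would raise the effect, but the documents give no rate of test-of-cure failure from which to size it.

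**The case against.** The strongest reply is that little depends on this. SAP 5.2.4 can be read as one row per woman, and then there is no clustering. Neither the number of repeats nor their correlation is given in the documents, and the likely effect on the standard error is small. With two or three non-resistant cases the interval is so wide that a few per cent does not matter. Section 7.7.1 also tabulates resistance by arm and visit, so results appear even if the model fails. The Protocol itself considers further selection of resistance in GC unlikely because resistance is already common.

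Most of this limits the size of the point without removing it. Section 7.7.1 speaks of cases, 2.2.5 adds test-of-cure swabs, and no rule reduces these to one per woman. The tabulations do not supply a pre-specified comparison between arms.

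A reader might also infer that the visit adjustment makes the model non-estimable, and that dropping it would be the cure. The documents and the check do not support that. The coding of visit is not stated, an infinite visit term can leave the arm odds ratio finite, and the arm estimate fails equally often without visit. The cause is the scarcity of non-resistant cases, which GEE does not cure either.

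**Conclusion.** The point holds in a limited form.

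**Clustering.** The omission in 7.7.1 is real and inconsistent with 7.7.2 and 7.5.1. It would be too strong to say that the interval is too narrow as a matter of fact. That requires several results per woman and positive correlation between them; under moderate assumptions the shortfall is about 1-10% of the standard error, and it is zero if one row per woman is analysed.

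**Sparse data.** This is the larger half, but it depends on tet(M) prevalence. Near 96% the stated model would give no finite arm odds ratio in about a third to two thirds of trials (34-63%) at N = 446. At 90% the share is 3-19%, and at 73% at most 0.3%. The 96% rests on 50 stored samples, so failure is a substantial risk and not a certainty.

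The two halves matter in different circumstances: clustering when there are enough non-resistant cases for the interval to be informative, sparse data when there are not. Neither touches the primary efficacy conclusion.

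**What to change.** Amend SAP 7.7.1 before database lock:

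1. State the unit of analysis. Do not count as a new case a test-of-cure re-positive within 28 days of treatment of a baseline or incident infection, in line with SAP 2.2.1.
2. When non-resistant cases are sufficient, use logistic GEE clustered on woman with robust standard errors, as in 7.7.2. If visit is kept, state its coding.
3. When non-resistant cases are sparse, analyse the first post-enrolment GC infection per woman by exact or Firth-penalised logistic regression on arm alone, and report the difference in proportions resistant with an exact interval. One infection per woman is needed here because ordinary exact and Firth methods assume independent observations.
4. Fix the cut-off for sparse in advance. This is a judgement. As a guide, if k non-resistant cases fall evenly at random between arms, one arm has none with probability 2 x 0.5^k: 25% for k = 3, 6% for k = 5 and 0.2% for k = 10. About 10 in total would be reasonable.

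If no non-resistant case occurs in either arm, no odds ratio method is informative, and the proportions alone should be reported.

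The cost is SAP wording, with no new data or tests. The downside is that repeat infections are dropped in the sparse case.
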